6.1.5 Model checking procedures

The appropriateness of the normality assumption of the combined APACHE II score will be assessed by graphical means e.g. residual plots.

6.1.6 Intercurrent events

As described in the primary estimand discontinuation of study treatment for any reason will be ignored.

6.1.7 Missing data

Missing data for the APACHE II score will be handled as follows:

- Missing values for age at screening will be replaced by using the stratification information assigning 3 points to participants up to 65 years (≤ 65 years) and 5 points to participants above 65 years.
- Missing information on acute renal failure status: use Serum Creatinine values without renal status information.
- Subscores of the Glasgow Coma Score (i.e. responses to Best Eye Response, Motor Response, Verbal Response) scored as “untestable”, “unknown” or missing will be replaced by the last available actual score. The response “untestable” is selected if the patient is unconscious (e.g. through sedation in case of mechanical ventilation).
- Missing values in any of the other parameters required for the derivation of the APACHE II score will be replaced by the last available assessment, as long as data is not carried forward by more than 4 days.

For a given visit, these missing data rules will only be applied if for at least one of the parameters contributing to the APACHE II score a value at this visit was reported.

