6.6.2 Recommended treatment of adverse events

Medication used to treat AEs must be recorded on the appropriate CRF.

Treatment of infection

In the event of an infection, Investigators should consider early treatment with specific antimicrobial therapy based on clinical diagnosis or suspicion thereof (e.g., anti-viral treatment for herpes simplex or zoster) in consultation with infectious disease experts, as appropriate.

Treatment of acute infusion and/or hypersensitivity reactions

As with most biologic compounds, CCI administration of MAS825 carries the risk of anaphylaxis and/or hypersensitivity-type reactions (see [Section 16.1](#)). In the event of such a reaction, Investigators should consider study-specific criteria for treatment discontinuation ([Section 9.1.1](#)), and the patient should be treated with antihistamines and glucocorticoids. Depending on severity, subjects may also require supplemental oxygen, volume expansion, catecholamines and transfer to an intensive care setting. Plasmapheresis to decrease the systemic concentration of MAS825 may be considered dependent on the patient’s condition. Subjects should be observed for at least four hours after resolution of signs and symptoms, and those who have experienced severe infusion reactions should be closely observed for 24 hours after resolution because of the risk for a biphasic episode.

Treatment of overdose

There is no clinical experience with MAS825 overdose. Should an overdose occur, the subject or patient should be carefully monitored for any potential symptoms, and if necessary, appropriate supportive care should be provided until the subject has recovered. The use of plasmapheresis may be considered to facilitate more rapid elimination of MAS825 from the peripheral circulation in the case of overdose.

At present there is insufficient information to provide specific recommendations regarding treatment of other potential adverse events (AEs) in this patient population. Acute kidney injury is common in patients with severe COVID-19. Treatment is supportive, with the institution of renal replacement therapy where this is indicated.

Medication used to treat adverse events (AEs) must be recorded on the appropriate CRF.

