10.2.1 APACHE II Scoring

Temperature (°C)

RSORRES	RSSTRESC	RSSTRESN
>=41	4	4
39-40.9	3	3
38.5-38.9	1	1
36-38.4	0	0
34-35.9	1	1
32-33.9	2	2
30-31.9	3	3
≤29.9	4	4

Mean Arterial Pressure (mmHg)

RSORRES	RSSTRESC	RSSTRESN
>=160	4	4
130-159	3	3
110-129	2	2
70-109	0	0
50-69	2	2
≤49	4	4

Heart rate (BEATS/MIN)

Does the participant have a pacemaker?	RSORRES	RSSTRESC	RSSTRESN
Irrespective	>=180	4	4
Irrespective	140-179	3	3
Irrespective	110-139	2	2
No/unknown	70-109	0	0
No/unknown	55-69	2	2
No/unknown	40-54	3	3
No/unknown	≤39	4	4
Yes	≤109	0	0

Respiratory rate (BREATHS/MIN)

Note: Ventilated or non-ventilated patient scores will be the same as per table below

RSORRES	RSSTRESC	RSSTRESN
>=50	4	4
35-49	3	3
25-34	1	1
12-24	0	0
10-11	1	1

6-9	2	2
<=5	4	4

Impute the unit for respiratory rate as breaths/min in case it is missing.Oxygenation:

- If $\text{FiO}_2 \geq 0.5$ then use A-aDO₂ (mmHg)

RSORRES	RSSTRESC	RSSTRESN
>=500	4	4
350-499	3	3
200-349	2	2
<200	0	0

- If $\text{FiO}_2 < 0.5$ then use PaO₂ (mmHg)

RSORRES	RSSTRESC	RSSTRESN
>70	0	0
61-70	1	1
55-60	3	3
<55	4	4

If any value for <X, impute the value X in that case.

Arterial pH

- Use arterial pH if reported

RSORRES	RSSTRESC	RSSTRESN
>=7.7	4	4
7.6-7.69	3	3
7.5-7.59	1	1
7.33-7.49	0	0
7.25-7.32	2	2
7.15-7.24	3	3
<7.15	4	4

- Alternatively use Serum HCO₃ (mmol/L)

RSORRES	RSSTRESC	RSSTRESN
>=52	4	4
41-51.9	3	3
32-40.9	1	1
22-31.9	0	0
18-21.9	2	2
15-17.9	3	3
<15	4	4

Serum sodium (mmol/L)

RSORRES	RSSTRESC	RSSTRESN
>=180	4	4
160-179	3	3
155-159	2	2
150-154	1	1
130-149	0	0
120-129	2	2
111-119	3	3
<=110	4	4

Serum potassium (mmol/L)

RSORRES	RSSTRESC	RSSTRESN
>=7	4	4
6-6.9	3	3
5.5-5.9	1	1
3.5-5.4	0	0
3-3.4	1	1
2.5-2.9	2	2
<2.5	4	4

Serum creatinine (mg/dL)

RSORRES	RSSTRESC	RSSTRESN
>=3.5 and acute renal failure ="yes"	8	8
2-3.4 and acute renal failure ="yes"	6	6
1.5-1.9 and acute renal failure="yes"	4	4
0.6-1.4 and acute renal failure ="yes"	0	0
<0.6 and acute renal failure ="yes"	4	4
>=3.5	4	4
2-3.4	3	3
1.5-1.9	2	2
0.6-1.4	0	0
<0.6	2	2

Hematocrit (%)

RSORRES	RSSTRESC	RSSTRESN
>=60	4	4
50-59.9	2	2

46-49.9	1	1
30-45.9	0	0
20-29.9	2	2
<20	4	4

White Blood Count ($10^9/L$)

RSORRES	RSSTRESC	RSSTRESN
≥ 40	4	4
20-39.9	2	2
15-19.9	1	1
3-14.9	0	0
1-2.9	2	2
<1	4	4

Age points (years)

RSORRES	RSSTRESC	RSSTRESN
≤ 44	0	0
45-54	2	2
55-64	3	3
65-74	5	5
≥ 75	6	6

Chronic health points

RSORRES	RSSTRESC	RSSTRESN
For non-operative or emergency post-operative patients	5	5
For elective post-operative patients	2	2

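### SAP 6.1.7 scores a blank acute renal failure status as *no* even when *yes* is on record, while creatinine itself is carried forward: a low-priority scoring gap in the primary endpoint

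*SAP*

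**What the plan says.** Protocol 12.4.4 leaves the handling of missing APACHE II components to the SAP. SAP 6.1.7 then sets rules by type of input:

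- **Acute renal failure status:** "Missing information on acute renal failure status: use Serum Creatinine values without renal status information".
- **Glasgow Coma subscores:** a missing or untestable value "will be replaced by the last available actual score", with no time limit stated.
- **All remaining parameters, which include creatinine:** a missing value "will be replaced by the last available assessment, as long as data is not carried forward by more than 4 days".

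The rules apply at a visit only if at least one APACHE II parameter was reported there. SAP 6.1.9 derives the primary endpoint, the combined APACHE II score at Day 15 or earlier discharge, after these rules have been applied. SAP 10.2.1 gives creatinine two sets of rows, one for acute renal failure *yes* and one with no mention of renal status.

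**The concern.** The rows without renal status are the ones a participant recorded as *no* would receive, so a blank is treated as *no*. Nothing in the rule looks back to an earlier *yes*. The status has its own bullet and therefore falls outside the carry-forward rule that covers creatinine.

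The two rules can split one piece of information. Suppose Day 14 has creatinine 3.8 mg/dL with status *yes*, and Day 15 has a temperature but no renal entries. Creatinine 3.8 is carried to Day 15 and the status is dropped. The same renal data then score 8 on Day 14 and 4 on Day 15, and the visible text gives no reason for the difference.

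What is at stake is a spurious improvement in the primary score, confined to participants with renal failure. The protocol itself notes in section 6.6.2 that "Acute kidney injury is common in patients with severe COVID-19". Because Protocol 5.2 excludes eGFR of 30 or below at entry, severe renal failure at Day 15 would mostly have arisen after randomization, so the baseline APACHE II covariate would not absorb the error.

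**Working it through.** **1. The plan's own figure.** Protocol 12.9.1 gives 60 per arm, difference 3.6, SD 9.2, one-sided alpha 10% and power 80%. The standard error of the difference is 9.2 × √(2/60) = 1.68. Power = Φ(3.6/1.68 − 1.282) = 80.6% (80.4% with the noncentral t), so the stated 80% is reproduced. It serves here only as a yardstick.

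**2. Loss per participant.** Points from SAP 10.2.1:

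| Creatinine (mg/dL) | Status *yes* | Status blank | Loss |
|---|---|---|---|
| ≥3.5 | 8 | 4 | 4 |
| 2-3.4 | 6 | 3 | 3 |
| 1.5-1.9 | 4 | 2 | 2 |
| 0.6-1.4 | 0 | 0 | 0 |
| <0.6 | 4 | 2 | 2 |

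**3. Effect on an arm mean.** Shift = proportion affected × loss. *Affected* means a known *yes*, a blank at the Day 15 or discharge visit, and creatinine outside 0.6-1.4. The documents do not give this proportion, so the values below are assumptions.

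| Proportion affected (assumed) | Fall in arm mean, at 2 to 4 points each | Upper value as share of 3.6 |
|---|---|---|
| 1% | 0.02-0.04 | 1.1% |
| 2% | 0.04-0.08 | 2.2% |
| 5% | 0.10-0.20 | 5.6% |
| 10% | 0.20-0.40 | 11.1% |

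As an illustration, if 15% of an arm had renal failure and one in five of those had a blank (both assumed), 0.15 × 0.20 = 3% would be affected. That is 1.8 of 60 participants, and the arm mean would fall by 0.06-0.12, at most 0.12/1.68 = 0.07 standard errors.

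**4. Effect on the comparison.** The bias in the difference is the shift in one arm minus the shift in the other. With equal rates and similar creatinine it is about zero. The extreme case puts every blank in one arm at 4 points each, with the SD held at 9.2:

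- **Placebo arm only:** the difference shrinks to 3.6 − 0.20 = 3.4 (5% affected) or 3.6 − 0.40 = 3.2 (10%). Power falls from 80.6% to 77.1% or 73.4%.
- **MAS825 arm only, no true effect:** one-sided type I error rises from 10% to 12.3% (5%) or 14.8% (10%).

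**5. Added noise.** If 3% are misscored by 4 points, the variance of the error is 0.03 × 0.97 × 16 = 0.47, against 9.2² = 84.6. This is negligible.

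**6. Is carry-forward feasible?** Protocol 8.3.2 has APACHE II parameters recorded every other day in hospital, and Table 8-1 lists both Day 14 and Day 15. The last recorded status will usually lie inside the 4-day limit.

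**The case against.** The strongest case for leaving the rule alone has four parts.

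- **It is an explicit, pre-specified choice.** SAP 6.1.7 deliberately sets different rules for different inputs, and renal status modifies the creatinine item instead of being one of the 14 summed items. This stands: a reader might infer that the SAP contradicts itself, but it does not. The criticism is that the rule discards a known status while keeping the creatinine value it belongs to.
- **Few participants can be affected.** The field is a simple yes/no. Protocol 11.2 provides for queries on missing values, and 11.3 requires full source verification of primary-variable data. Deaths by Day 15 take the worst observed score instead. SAP 6.1.2 also summarizes the sub-scores. This stands as a reason for low priority, although none of it changes the scoring of a blank that remains.
- **Bias needs an arm difference.** A reader might infer that the rule shrinks real treatment differences even when renal failure and blanks are equally common in both arms. The arithmetic does not support this, because a common offset cancels in the difference of means.
- **Carry-forward has the opposite error.** A participant improving from creatinine 3.8 to 1.6 mg/dL, with a blank status after an earlier *yes*, would score 4 instead of 2. This is a genuine cost, and the documents do not settle which error is more frequent. But the SAP already accepts stale values of up to 4 days for its other carried-forward inputs.

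**Conclusion.** The point holds as a minor inconsistency in the scoring of the primary endpoint. For a participant with a known *yes* and a blank at the visit that counts, the loss is 4, 3, 2 or 2 points by creatinine band and 0 at 0.6-1.4 mg/dL, always toward less severe disease. These figures follow directly from SAP 10.2.1. The arm-mean shift of about 0.02-0.4 points rests on an assumed 1-10% affected, and the comparison is biased only to the extent that the arms differ.

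Two larger readings should be avoided. It would be wrong to say that participants with renal failure in general lose 2-4 points: the status must be blank at the Day 15 or discharge visit, and creatinine must be outside 0.6-1.4. It is also tempting to set one participant's 4 points against the planned effect of 3.6, but that effect is a difference between group means, so the two are not comparable.

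There is one knock-on route. Deaths by Day 15 receive the highest observed score in the trial, so an understated score could lower that value if it belonged to the top scorer. The documents give no means of judging how likely that is.

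**What to change.** Replace the bullet in SAP 6.1.7 with: *if acute renal failure status is missing at a visit, carry forward the last recorded status within the 4-day limit used for other parameters; if none is available, score creatinine without renal status.*

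Need for CRRT, which Table 8-1 schedules at every visit, may be used as supporting information in a sensitivity analysis. Setting the status to *yes* from CRRT in the primary analysis is more debatable and is not needed to close the gap. A blinded count of blanks before database lock would show whether the rule matters at all.

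The cost is one SAP sentence and a small programming change, with no new data. The downside is that a resolved renal failure could be carried for up to 4 days.

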12.9 Sample size calculation

12.9.1 Primary endpoint(s)

The sample size is limited to maximum of 60 participants to be treated with a single i.v.dose of MAS825 due to limitations in the available drug supply at this point in time. To establish clinical efficacy based on APACHE II score a sample size of 60 participants per treatment group provides 80% power when testing on an 10% 1-sided alpha level under the assumption that MAS825 reduces the APACHE II score by 3.6 points more than placebo (assumed standard deviation of 9.2 based on [Yang et al 2020](#)).

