16.4 Appendix 4: ICU scores

Table 16-3 APACHE II

	Variable	Unit
	Age	years
	Glasgow Coma Score	
Vitals	Body temperature	°C
	Mean arterial pressure (MAP)	mmHg
	Heart rate	bpm
	Respiratory rate	breaths/m
Oxygenation	FiO ₂	%
	PaO ₂	mmHg
	Arterial pH	
	PaCO ₂	mmHg
	Altitude of site	Meters above sea level
Chemistry	Sodium	mEq/L
	Potassium	mEq/L
	Creatinine	mg/dL
	Acute Renal Failure	Yes/No
Hematology	Hematocrit	%
	White blood cell (WBC) count	×10 ⁹ /L
	Severe organ system insufficiency or is immunocompromised	Yes/No

Source: (Knaus et al 1985)

Table 16-4 Estimating PaO₂ from a given SpO₂

SpO ₂ (%)	PaO ₂ (mmHg)
80	44
81	45
82	46
83	47
84	49
85	50
86	52
87	53
88	55
89	57
90	60
91	62
92	65
93	69
94	73
95	79
96	86
97	96
98	112
99	145

Source : ([Vincent et al 2009](#))

Table 16-5 Estimating FiO₂

Method	O ₂ flow (l/min)	Estimated FiO ₂ (%) [*]
Nasal cannula	1	24
	2	28
	3	32
	4	36
	5	40
	6	44
Nasopharyngeal catheter	4	40
	5	50
	6	60
Face mask	5	40
	6-7	50
	7-8	60
Face mask with reservoir	6	60
	7	70
	8	80
	9	90
	10	95

Source : ([Vincent et al 2009](#))

* If patient is breathing air then estimated FiO₂ is 21%

Commercially Confidential Information

Table 16-8 GLASGOW COMA SCORE

Eye Opening

Criterion	Rating	Score
Open before stimulus	Spontaneous	4
After spoken or shouted request	To sound	3
After finger tip stimulus	To pressure	2
No opening at any time, no interfering factor	None	1
Closed by local factor	Non testable	NT

Verbal Response

Criterion	Rating	Score
Correctly gives name, place and date	Orientated	5
Not orientated but communication coherently	Confused	4
Intelligible single words	Words	3
Only moans/groans	Sounds	2
No audible response, no interfering factor	None	1
Factor interfering with communication	Non testable	NT

Best motor response

Criterion	Rating	Score
Obey 2-part request	Obeys commands	6
Brings hand above clavicle to stimulus on head/neck	Localising	5
Bends arm at elbow rapidly, but features not predominantly abnormal	Normal flexion	4
Bends arm at elbow, features clearly predominantly abnormal	Abnormal flexion	3
Extends arm at elbow	Extension	2
No movement in arms/legs, no interfering factor	None	1
Paralysed or other limiting factor	Non testable	NT

Source: (Teasdale and Jennett 1974)

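### SAP 6.1.7 treats unconsciousness as untestable on the Glasgow Coma Score, so coma with no interfering factor can be under-scored by up to 12 points in the primary endpoint

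*SAP*

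**What the plan says.** The primary endpoint for a participant still in hospital at Day 15 is the Day 15 APACHE II score after the missing-data rules (SAP 6.1.9). The Glasgow item enters as 15 minus the Glasgow total (SAP 10.2).

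Under SAP 6.1.7, a Glasgow sub-score that is untestable, unknown or missing takes the last score actually recorded. The same bullet says that untestable "is selected if the patient is unconscious (e.g. through sedation in case of mechanical ventilation"). The next bullet covers the remaining parameters and allows carry-forward only "as long as data is not carried forward by more than 4 days". The Glasgow bullet has no such limit. The one general guard is that at least one APACHE II parameter was reported at that visit.

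Protocol Table 16-8 gives the lowest eye score, 1, for "No opening at any time, no interfering factor", and treats verbal and motor responses in the same way. It keeps the non-testable category for an interfering cause; for the motor item this is "Paralysed or other limiting factor". SAP 10.5.1 also gives 1 for no eye, motor or verbal response, and lists untestable separately without defining it.

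**The concern.** Coma in a participant who is neither sedated, intubated nor paralysed can be observed, and both scoring tables give it a value. SAP 6.1.7, read as written, turns that value into a missing one and fills it with an earlier and probably better score. Protocol 12.4.4 leaves missing APACHE II components to the SAP, but an observed absence of response is not missing.

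Glasgow is the largest single item in the score, at up to 12 points; the next is creatinine with acute renal failure, at 8 (SAP 10.2.1). Intubated patients are excluded at entry (Protocol 5.2), so a good early Glasgow score is plausible, and it could be carried about 14 days from baseline to Day 15. The estimand is meant to include the effect in patients who stay in hospital, and this rule can hide neurological deterioration in exactly that group.

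**Working it through.** **1. The plan's own figure.** Protocol 12.9.1 states "a sample size of 60 participants per treatment group" for "80% power when testing on an 10% 1-sided alpha level", assuming that MAS825 "reduces the APACHE II score by 3.6 points more than placebo", with an "assumed standard deviation of 9.2".
- n per arm = 2 × (1.282 + 0.842)² × (9.2 / 3.6)² = 58.9, so 59.
- Standard error with 60 per arm = 9.2 × √(2/60) = 1.680. Power = Φ(3.6 / 1.680 − 1.282) = Φ(0.86) = 80.6% (80.4% with the noncentral t).

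The planned size reproduces.

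**2. The scoring rules side by side.**

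| Participant | Protocol Table 16-8 | SAP 10.5.1 | SAP 6.1.7 |
|---|---|---|---|
| Unconscious, no interfering factor | 1 + 1 + 1 = 3 | 1 + 1 + 1 = 3 | Untestable; last recorded score used |
| Sedated and ventilated | Verbal and motor can be non-testable; eye only if closed by a local factor | Untestable is available but undefined | Untestable; last recorded score used |

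The first row is a conflict. The second is mostly consistent; only the eye item is doubtful.

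**3. Size for one participant in the first row.**
- Points under the tables: 15 − 3 = 12.
- Points under 6.1.7 with a last total of 15: 15 − 15 = 0. Loss: 12.
- With a last total of 11: 15 − 11 = 4 points kept. Loss: 8.

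**4. Effect on the treatment difference.** Shift = points lost × net between-arm difference in participants affected / 60.
- One extra participant at the ceiling: 12 × 1/60 = 0.2 points; 0.2 / 3.6 = 5.6%.
- One extra participant at a loss of 8: 8 × 1/60 = 0.13 points.
- Extra participant on placebo: the difference falls from 3.6 to 3.4 and power becomes Φ(3.4 / 1.680 − 1.282) = Φ(0.74) = 77.1%.
- Extra participant on MAS825: the apparent difference rises from 3.6 to 3.8.
- Equal numbers in both arms: no shift in the mean difference.

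The power figure holds the standard deviation at 9.2. The documents give no share affected, so the net number is left as a unit and not estimated.

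**5. Is the rule tested anywhere?** The sensitivity analysis in SAP 6.1.4 changes only the analysis set. In the visible text of SAP 6.1.10, analysis 1 reuses the same combined score and analyses 2 to 4 use scores after the same missing-data rules. Part of 6.1.10 is redacted. No visible analysis varies the Glasgow rule.

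**The case against.** The strongest case for the plan is that the rule was written for sedated, ventilated participants. For them a pre-sedation score is a reasonable choice, because drug-induced unresponsiveness is arguably not disease severity, and Table 16-8 has non-testable categories that can cover intubation and sedation for the verbal and motor items. This stands, and the conflict is confined to unconsciousness without an interfering factor.

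The missing time limit can also be defended. One missing item makes the whole score missing (SAP 10.2), so a 4-day limit could cost longer-sedated participants their Day 15 score. The SAP does not give this reason, but it is a fair argument against simply importing the limit.

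Other points limit the size. Only the Glasgow item is affected, and the other items still register deterioration. Deaths by Day 15 are handled separately. Need for invasive ventilation is captured by a secondary endpoint. SAP 6.1.2 summarises the sub-scores, so an odd Glasgow pattern might be noticed, though that is not a sensitivity analysis.

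A reader might infer three stronger things that the documents do not support:
- **That a large part of the planned effect is hidden.** A gap of 5 to 10 percentage points in untestable participants (3 to 6 of 60) at 12 points each would give 0.6 to 1.2 points. That counts sedated participants, for whom carry-forward is defensible, puts everyone at the ceiling, and assumes a gap that the documents do not give.
- **That the last awake score is carried.** The SAP carries the last recorded score, which may already be impaired. Entry requires an APACHE II score of at least 10 and allows consent by a representative, so a reduced baseline Glasgow score is possible.
- **That a benefit of MAS825 is removed from the endpoint.** The mean difference shifts only if the arms differ in the number affected, and the shift can go either way.

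**Conclusion.** The rule in SAP 6.1.7 is wrong as written for one group: participants unconscious with no interfering factor. For them it contradicts Protocol Table 16-8 and SAP 10.5.1 and can under-score the primary endpoint by up to 12 points each. At trial level the direct effect is at most 0.2 points per net participant of imbalance, about 6% of the planned difference, with unknown direction and no shift if the arms are equal.

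This assumes 60 analysed per arm and counts only the direct effect. Deaths receive the highest score observed in the trial, and the SAP does not say whether scores with imputed items count, so a knock-on effect through that value is possible and is not quantified here.

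For sedated or intubated participants the carry-forward itself is acceptable. What remains open is that it has no limit, no stated reason for having none, and no visible analysis showing whether the result depends on it.

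**What to change.** - Reword SAP 6.1.7 and the CRF guidance to agree with Table 16-8 and SAP 10.5.1: score unconsciousness without an interfering factor as observed, and carry a Glasgow sub-score forward only when a factor such as sedation, intubation or paralysis is recorded.
- State in 6.1.7 whether the absence of a Glasgow carry-forward limit is intended, and why.
- Pre-specify one sensitivity run of the primary ANCOVA with every untestable sub-score set to 1. This is a bound and not a preferred estimate, because it also gives sedated participants the worst score.
- Report by arm how many Day 15 or discharge scores use carried-forward Glasgow values, and for how many days.

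The cost is SAP wording, CRF guidance, one model run and one table. If the CRF does not already record the interfering factor, one field is needed; the documents do not show this.
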